7 INVESTIGATIONAL PLAN

7.1 Overall Study Design and Plan

7.1.1 Description

This is an open-label, Phase 2 study to evaluate the safety, tolerability, PK, and PD effects of 3 dose levels of A3907, 10 mg (Arm 1), 30 mg (Arm 2) administered orally QD, or 30 mg BID in Arms 3 and 4 for 12 weeks in patients with PSC with and without a CRS (Figure 1). Eligible patients must have a clinical diagnosis of large-duct- PSC as evidenced by chronic cholestasis of more than 6 months duration. Patients must also have serum bile acids above the upper limit of normal (ULN) at the Screening Visit and ALP levels $> 1.5 \times \text{ULN}$ but $\leq 10 \times \text{ULN}$ repeated at least 2 weeks apart for baseline to reflect variability of $< 30\%$. If variability is $> 30\%$, a third ALP level may be obtained to determine the direction of abnormality or document stability. If stable ($< 30\%$ variance) the patient may be enrolled.

Prior to any other study procedures being conducted, the patient will have the nature of the study explained to him/her and be asked to sign an informed consent form (ICF). Informed consent must be obtained prior to any study procedures that do not form a part of the patient's normal care. After signing the ICF, patients will be evaluated for study eligibility. If not fasting at time of consent, patient will return to complete screening assessments after having fasted for 4 hours.

The study includes up to a 2-week Screening Period, followed by administration of a single dose of A3907, followed by a 2-week period to confirm the target exposure is reached before beginning a treatment period of 12 weeks. Each patient's PK will be reviewed and, if the systemic exposures do not exceed the highest systemic exposure previously established in the SAD portion of the FIH study CCI

CCI the dose will be confirmed and the patient will begin administration of A3907 daily for 12 weeks. If the exposures exceed the highest systemic exposure, the individual patient will be terminated early.

Enrollment into the treatment arms will be staggered with Arm 2 beginning after at least 3 patients in Arm 1 have completed 2 weeks of treatment and an internal Safety Review Committee (SRC) has reviewed safety and PK data. Enrollment into Arms 3 and 4 will occur

[figure not shown]
concurrently beginning after at least 3 patients in Arm 2 have completed 2 weeks of treatment and an internal SRC has reviewed safety and PK data.

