12. If a patient has IBD with a minimum disease duration of 4 weeks, this diagnosis should be documented. Inflammatory bowel disease should be in clinical remission or mildly active according to Crohn's Disease Activity Index (CDAI), partial Mayo score for Crohn's Disease (CD and ulcerative colitis (UC), respectively (i.e. patients with CDAI score < 220 and Mayo score < 5 , respectively). Patients with IBD should have had a colonoscopy performed within one year prior to the Screening Period with results showing no evidence of dysplasia or cancer.
13. Clinically stable for at least 3 months prior to the Screening Period

14. Arm 4 Only: One stable clinically relevant biliary stricture of at least 4 weeks duration on contrast-enhanced MRI/MRCP with > 75% reduction of duct diameter in the common bile duct or hepatic duct without suspicion of cholangiocarcinoma (further established by imaging and stable CA 19-9 below ULN repeated twice over 1 month), or cholelithiasis. Subjects may have signs or symptoms of worsening obstructive cholestasis (increasing jaundice, nausea, anorexia, steatorrhea and worsening or new onset pruritus), deterioration of liver function (i.e. decreasing platelet count, increasing international normalized ratio [INR]) and/could be listed for liver transplantation due to their clinically relevant biliary stricture.
15. Arm 4 Only: MELD Score < 35

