7.2.3 Exclusion Criteria

Patients meeting any of the following criteria will be excluded from the study:

Medical History

1. Presence of documented secondary sclerosing cholangitis (such as ischemic cholangitis, recurrent pancreatitis, intraductal stone disease, severe bacterial cholangitis, surgical or blunt abdominal trauma, recurrent pyogenic cholangitis, choledocholithiasis, toxic sclerosing cholangitis due to chemical agents, or any other cause of secondary sclerosing cholangitis).
2. Arm 1-3 Only: Biliary intervention within 3 months prior to study enrollment or planned.
3. Arm 4 Only: Planned Biliary intervention between the Screening Period and baseline.
4. Presence of alternative causes of chronic liver disease, including alcohol-associated liver disease, nonalcoholic steatohepatitis, primary biliary cholangitis, autoimmune hepatitis, or active hepatitis B or C.
5. IBD with uncontrolled moderate to severe activity and/or on treatment with any immunosuppressive, immunomodulator, or biologic agent for treatment of IBD (i.e. azathioprine, 6 mercaptopurine, tacrolimus, methotrexate, infliximab, adalimumab, golimumab, vedolizumab, ustekinumab, tofacitinib, ozanimod). Treatment with corticosteroids (including budesonide, budesonide MMX and beclomethasone) in the previous 4 weeks.
6. History of human immunodeficiency virus infection or any other known relevant infection (e.g. tuberculosis).
7. History of ileectomy, colostomy or colectomy.

8. History of malignancy, including hepatocellular carcinoma and cholangiocarcinoma within the past 10 years, except for basal or squamous cell carcinoma of the skin or carcinoma in situ of the cervix that has been successfully treated.
9. Alpha-fetoprotein (AFP) > 20 ng/mL (at the Screening Visit) with 4-phase liver CT or MRI suggesting presence of liver cancer.
10. History of transplants, including liver transplantation, or currently on active transplantation list (Arms 1-3). Arm 4 may be on an active liver transplantation list.
11. Current or a history of hepatic decompensation events including, but not limited to ascites, encephalopathy, or history of esophageal variceal bleeding.
12. Known or suspected overlapping clinical and histologic diagnosis of autoimmune hepatitis.
13. Small duct PSC (evidence of PSC on historical liver histology, with normal bile ducts on cholangiography) without large duct PSC.
14. Liver cirrhosis as assessed by any of the following:
 - a. historical liver histology.

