 - b. liver stiffness measurement, assessed by FibroScan (FibroScan value > 14.4 kPa), in addition to clinical assessment and biochemical markers at the discretion of the investigator.
 - c. signs and symptoms of hepatic decompensation (including, but not limited to, jaundice, ascites, variceal haemorrhage, and/or hepatic encephalopathy).
15. History of bacterial cholangitis within 60 days prior to the Screening Period, or if the patient is on antibiotics for prophylaxis of recurrent cholangitis.
16. Females who are pregnant, lactating, or breast feeding as detailed in [Section 9.3.18](#).
17. History of alcohol or substance abuse in the previous 2 years. Patients must agree to refrain from illicit drug (including marijuana) and alcohol use during the study.
18. Hypersensitivity to investigational medicinal product (A3907) and its excipients.
19. Presence of any contraindication for undergoing MRCP (e.g. pacemaker).
20. Any other condition or abnormality which, in the opinion of the investigator (or designee), may compromise the safety of the patient or interfere with the patient participating in, or completing the study.

Treatment Exclusions:

21. Administration of medications that slow gastrointestinal motility ([Section 8.6.2](#)).
22. Treatment with rifampicin.

23. Exposure to oral drugs that are strong inhibitors or inducers of CYP3A4 enzymes (e.g. grapefruit juice, ritonavir, itraconazole, ketoconazole, troleandomycin, rifampin, St John's wort, etc.) within 14 days prior to the Screening Period, or 5 half-lives of the drug, whichever is longer ([Section 8.6.2](#)).
24. Exposure to oral drugs that are substrates of CYP3A4 enzymes (e.g. codeine, ciclosporin [cyclosporin], diazepam, etc.) during the study ([Section 8.6.2](#)).
25. Treatment with vitamin D or fibrates, unless patient is on a stable dose ≥ 6 months prior to baseline.
26. Exposure to an investigational drug, biologic agent, or medical device within 30 days prior to the Screening Period, or 5 half-lives of the study agent, whichever is longer.

Laboratory Exclusions:

27. Platelet count $< 150\,000/\text{mm}^3$.
28. Albumin level $< 3.0\text{ g/dL}$.
29. INR > 1.3 (the patient may be treated with vitamin K intravenously, and if INR is ≤ 1.3 at resampling, the patient may be enrolled).
30. Medical conditions that may cause non-hepatic increases in ALP (e.g. Paget's disease). A GGT or ALP isoenzymes should be obtained for confirmation of biliary origin;

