	Visit 8	Follow-Up after 12-Week Treatment	112	\geq last dose day* + 8
URINE SAMPLING FOR INDIVIDUAL AND TOTAL BILE ACIDS	Visit 2	Baseline		≤ 1 (24-hour Pre-Dose period)
	Visit 3	Start of 12-Week Treatment	14	Post-baseline – 29
	Visit 5	Week 4 of 12-Week Treatment	42	30 – 71
	Visit 7	Week 12 of 12-Week Treatment	98	72 – last dose day* + 7
	Visit 8	Follow-Up after 12-Week Treatment	112	\geq last dose day* + 8
HEMATOLOGY	Visit 1	Baseline		≤ -1 (Pre-dose)
	Visit 3	Start of 12-Week Treatment	14	Post-baseline – 22

ASSESSMENT(S)	TIMING OF ASSESSMENT	VISIT NAME TO DISPLAY FOR ANALYSIS	TARGET DAY	ANALYSIS WINDOW (STUDY DAY)
	Visit 4	Week 2 of 12-Week Treatment	28	23 – 36
	Visit 5	Week 4 of 12-Week Treatment	42	37 – 57
	Visit 6	Week 8 of 12-Week Treatment	70	58 – 85
	Visit 7	Week 12 of 12-Week Treatment	98	86 – last dose day* + 7
	Visit 8	Follow-Up after 12-Week Treatment	112	≥ last dose day* + 8
Pruritus NRS lead question	Visit 1	Baseline		≤ -1
COAGULATION	Visit 1	Baseline		≤ -1
	Visit 3	Start of 12-Week Treatment	14	Post-baseline – 29
	Visit 5	Week 4 of 12-Week Treatment	42	30 – 71
	Visit 7	Week 12 of 12-Week Treatment	98	72 – (last dose day* + 7)
12 LEAD ECG	Visit 1	Baseline		≤ -1
	Visit 2	Baseline		1 (Pre-dose)
	Visit 5	Week 4 of 12-Week Treatment	42	Post-baseline – 71
	Visit 7	Week 12 of 12-Week Treatment	98	72 – (last dose day* + 7)
ENDOSCOPIC BILIARY DILATION DATA	Visit 2	Baseline		≤1 (Pre-dose)
	Visit 7	Week 12 of 12-Week Treatment	98	Post-baseline – (last dose day* + 7)

ASSESSMENT(S)	TIMING OF ASSESSMENT	VISIT NAME TO DISPLAY FOR ANALYSIS	TARGET DAY	ANALYSIS WINDOW (STUDY DAY)
PHYSICAL EXAMINATION	Visit 1	Baseline		≤ -1
	Visit 2	Baseline		1 (Pre-dose)
	Visit 5	Week 4 of 12-Week Treatment	42	Post-baseline – 71
	Visit 7	Week 12 of 12-Week Treatment	98	72 – (last dose day* + 7)
	Visit 8	Follow-Up after 12-Week Treatment	112	\geq last dose day* + 8
FAECAL CALPROTECTIN	Visit 2	Baseline		≤ 1 (Pre-dose)
	Visit 3	Start of 12-Week Treatment	14	Post-baseline – 22
	Visit 4	Week 2 of 12-Week Treatment	28	23 – 36
	Visit 5	Week 4 of 12-Week Treatment	42	37– 57
	Visit 6	Week 8 of 12-Week Treatment	70	58– 85
	Visit 7	Week 12 of 12-Week Treatment	98	86 – (last dose day*+7)
	Visit 8	Follow-Up after 12-Week Treatment	112	\geq last dose day*+8
FIBROSCAN	Visit 1	Baseline		≤ -1
	Visit 3	Start of 12-Week Treatment	15	Post-baseline – 29
	Visit 5	Week 4 of 12-Week Treatment	43	30 – 71
	Visit 7	Week 12 of 12-Week Treatment	99	72 – (last dose day* + 7)

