9.6. Episodes of cholangitis requiring Antibiotic use

A summary table of the patients with episodes of cholangitis requiring antibiotic use in the 12 weeks prior to single dosing versus the 12-week treatment period will be presented for the Safety Analysis Set. Baseline 1 is defined as data collected on the day of the planned single dose, which are assessments of 12 weeks prior to Single Dosing. Supporting listing will also be presented for the Safety Analysis Set.

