9.8. Endoscopic biliary dilation intervals/frequency

For Arm 4, a summary table of endoscopic biliary dilation intervals/frequency will be presented for the Safety Analysis Set. The absolute and relative change in the 12 weeks prior to single dosing (V2) compared to the 12-week treatment period (V7) table will also be presented for the Safety Analysis Set. Baseline 1 is defined as data collected on the day of the planned single dose, which are assessments of 12 weeks prior to Single Dosing. Supporting listing will also be presented for the Safety Analysis Set.

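### Entry criteria leave only 24 of the 84 pre-dose days open to bacterial cholangitis, so the before/after table in SAP 9.6 is expected to show an increase even on an inert drug

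*SAP*

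**What the plan says.** **Cholangitis.** SAP 9.6 compares "episodes of cholangitis requiring antibiotic use in the 12 weeks prior to single dosing versus the 12-week treatment period", in the Safety Analysis Set, which is everyone who took one dose. It gives no time-at-risk denominator and no restriction to patients who started the 12-week period. The objective in Protocol 6.1.3 and SAP 2.3 covers only patients with 12 weeks of pre-dose data; SAP 9.6 does not repeat that limit.

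Three entry rules bear on the pre-dose window:
- Exclusion 15, all arms: "History of bacterial cholangitis within 60 days prior to the Screening Period, or if the patient is on antibiotics for prophylaxis of recurrent cholangitis".
- Inclusion 13, all arms: "Clinically stable for at least 3 months prior to the Screening Period". The protocol does not define stability.
- Protocol 7.1.1: "The study includes up to a 2-week Screening Period". Visit 1 is at Day −14 (±2).

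**Dilation, Arm 4 only.** SAP 9.8 plans "The absolute and relative change in the 12 weeks prior to single dosing (V2) compared to the 12-week treatment period (V7) table". The protocol endpoint is limited to patients who are dilated regularly. The relevant entry rule is Exclusion 3: "Arm 4 Only: Planned Biliary intervention between the Screening Period and baseline". In SAP 4.5, Table 2 gives the Visit 7 window for dilation data as "Post-baseline – (last dose day* + 7".

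**The concern.** The two periods in SAP 9.6 have the same nominal length but not the same opportunity for events. Patients are admitted because most of the first period was quiet, and no such condition applies to the second. A return to each patient's usual rate will then look like an increase on drug.

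This matters because the study is uncontrolled, its primary objective is safety, and the protocol itself describes cholangitis as a common biliary complication of PSC. The table could be read as a safety signal that the design produced, or it could hide a real reduction. Nothing in the SAP warns the reader.

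The missing denominator adds a second distortion. Patients stopped after the single dose, for example because of high exposure, contribute 12 weeks before dosing and nothing to the treatment period. For MELD, FibroScan and the Mayo score, the SAP limits its treatment-period (baseline 2) summaries to patients who entered that period; SAP 9.6 and 9.8 do not.

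**Working it through.** The plan states no rate, expected count or ratio for these endpoints, so there is no figure to reproduce. The check counts days at risk.

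**Cholangitis: inputs.** Pre-dose window 12 × 7 = 84 days (SAP 9.6). Treatment period 84 days. Required episode-free time 60 days before Screening (Exclusion 15). Screening up to 14 days, or 12 to 16 with the visit window.

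**Open pre-dose days.** The 60 closed days lie wholly inside the 84-day window for any screening length up to 84 − 60 = 24 days, so the answer does not depend on the actual screening length:
- closed: 60/84 = 71%
- open: 84 − 60 = 24 days (with a 14-day screening, the 14 screening days plus the 10 earliest days)

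**Expected episode ratio with no drug effect.** If each patient's own rate is constant, the ratio is the ratio of open days and does not depend on the level of the rate:
- Exclusion 15 alone: 84/24 = 3.5
- Inclusion 13 also read as barring episodes for 3 months before a 14-day screening, so only screening is open: 84/14 = 6

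**Patients with an episode.** SAP 9.6 counts patients. The documents give no rate, so rates are assumed. With 24 patients and rate r per patient-year, expected episodes are 24 × r × d/365.25 and expected patients are 24 × (1 − exp(−r × d/365.25)), with d = 24 before dosing and d = 84 on treatment. Ratios use unrounded counts.

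| Assumed r | Episodes pre / on | Patients pre / on | Patient ratio |
|---|---|---|---|
| 0.1 | 0.16 / 0.55 | 0.16 / 0.55 | 3.5 |
| 0.5 | 0.79 / 2.76 | 0.78 / 2.61 | 3.4 |
| 1.0 | 1.58 / 5.52 | 1.53 / 4.93 | 3.2 |
| 2.0 | 3.15 / 11.04 | 2.96 / 8.85 | 3.0 |

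At r = 0.1 the chance of no episode in either period is exp(−(0.16 + 0.55)) = 0.49.

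**Time at risk.** If m of N patients never enter the 12-week period, the episode ratio becomes 3.5 × (N − m)/N. This runs the other way, but on-treatment time would have to fall to 24/84 = 29% of plan before the two distortions cancelled.

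**Dilation: eligibility.** Exclusion 3 closes about 14 of 84 days (17%), to planned procedures only. The ratio with no drug effect is at most 84/(84 − 14) = 1.2; for 12 to 16 days of screening it is 84/72 = 1.17 to 84/68 = 1.24.

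**Dilation: window.** In SAP day numbering the single dose is Day 1 and the planned last dose is Day 99, so Table 2 runs from Day 2 to Day 106, which is 105 days. Counting 105 days against 84 would give 105/84 = 1.25 with no drug effect and no eligibility gap.

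**The case against.** **Importance.** Both endpoints are exploratory and summarised descriptively. No test or decision rule depends on them, and the primary endpoint, TEAE incidence, is untouched. This stands and limits the weight of the point.

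**Small counts.** At low rates, none before and none after is a likely result. This also stands: the increase is an expectation, not a guarantee.

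**Direction.** The cholangitis bias points towards harm, so it cannot create a false benefit. True, but it can conceal a real one: a drug that halved the rate would still have an expected ratio of 3.5 × 0.5 = 1.75.

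**Protocol endpoint.** The before/after contrast is defined in Protocol 6.2.3, so dropping it is more than an edit to SAP wording. This stands, and the fix records the departure.

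Several stronger readings are tempting, but the documents do not support them.
- *Eligibility also empties the dilation pre-period.* The three-month exclusion of biliary interventions covers Arms 1 to 3 only, and the endpoint is Arm 4 only. Regularly dilated patients will have pre-dose dilations by definition, and choosing them could even bias the other way.
- *The dilation ratio is 105/70 = 1.5.* This needs the Table 2 window to serve as the counting period. SAP 4.5 presents those windows as rules for assigning visit labels, while SAP 9.8 names the 12-week period. Unplanned dilations are also allowed throughout screening.
- *A patient dilated every 4 weeks loses procedures to the screening gap.* A fixed 28-day schedule can fit around a 14-day gap. With the last dilation 14 to 28 days before dosing, the earlier ones fall at 42–56 and 70–84 days, making 3. Later ones fall at protocol Days 28–42, 56–70 and 84–98, making 3 in the 12-week period. Only shorter intervals must lose any.
- *The cholangitis ratio is 84/10 = 8.4, because an episode during screening would also prevent entry.* Exclusion 15 covers the time before Screening, and no criterion names an episode during it.
- *The dilation pre-period could simply end at Visit 1.* Dilation data are documented there, but the SAP describes a 12-week look-back only for the record on the single-dose day.

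**Conclusion.** The point holds for cholangitis. Exclusion 15 closes 71% of the pre-dose window, so SAP 9.6 is expected to show about 3.5 times as many episodes on an inert drug, up to about 6 under the stricter reading of Inclusion 13. As patients with an episode, the ratio is about 3.0 to 3.4 at 2 to 0.5 episodes per patient-year.

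This assumes a constant rate within each patient, that the counted episodes are bacterial (the endpoint requires antibiotic use, while the exclusion names bacterial cholangitis), and full follow-up on treatment. The rates are assumptions; the episode ratio of 3.5 does not depend on them. Using the whole Safety Set without time at risk is a separate defect that partly offsets the first, by an amount that depends on discontinuation.

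For dilation, eligibility accounts for a ratio of at most about 1.2. What remains is an inconsistency between Table 2 and SAP 9.8 that would be worth 1.25 if Table 2 governed the count.

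A correction in the SAP is worth making. No confirmatory conclusion is at risk.

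**What to change.** **SAP 9.6.** Do not present the before/after difference as a drug effect. Report on-treatment episodes per 12 patient-weeks at risk, with an exact 95% CI, in patients who entered the 12-week period. List pre-dose episodes with a footnote saying that Exclusion 15 requires the 60 days before Screening to be free of bacterial cholangitis.

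**SAP 9.8 and Table 2.** State which period is counted after dosing. Report dilations per 28 days at risk from first to last dose of the 12-week period, and footnote the restriction that Exclusion 3 places on the pre-dose period.

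**SAP section 11.** Record the departure from the protocol's exploratory cholangitis endpoint.

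**Cost.** SAP text and modest changes to two tables, with no new data collection. What is lost is an exploratory contrast that could not have been interpreted.

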6.1.3 Exploratory Objectives

The exploratory objectives are:

- To explore the effect of A3907 on markers of liver inflammation and fibrosis
- To evaluate the effect of A3907 on symptoms
- To explore the effect of A3907 on episodes of cholangitis (for patients with available 12-week data prior to dosing)

Additional Exploratory Objectives, Arm 4 Only:

- To evaluate the effects of A3907 on survival without a liver transplant
- To evaluate the effect of A3907 on bile duct function

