2.3. Exploratory Objectives

- To explore the effect of A3907 on markers of liver inflammation and fibrosis.
- To evaluate the effect of A3907 on symptoms.
- To explore the effect of A3907 on episodes of cholangitis (for patients with available 12-week data prior to single dosing).

Additional exploratory objectives, Arm 4 only:

- To evaluate the effects of A3907 on survival without a liver transplant.
- To evaluate the effect of A3907 on bile duct function

3. Investigational Plan

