displayed to two levels of precision greater than the data collected up to a maximum of three decimal places. A row denoted “Missing” will be included in count tabulations where specified on the shells to account for dropouts and missing values. The denominator for all percentages will be the number of patients in that treatment arm within the population of interest, unless otherwise specified. Refer to the [Appendix 1](#) for imputation rules for partial and missing AE onset dates as well as partial and missing prior/concomitant medication start and end dates. Data will be displayed in all listings sorted by treatment arm.

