4.3.3. Safety Analysis Set

The safety analysis set will include all patients who received at least 1 dose of A3907 and will be used for all analyses except PK and PD analyses.

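### The cholangitis before/after table in SAP 9.6 omits the objective's limit to patients with a 12-week pre-dose history and names no denominator, so patients unobserved in a period can lower that period's percentage

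*SAP*

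**What the plan says.** The objective carries a restriction in both documents. Protocol 6.1.3 states it "for patients with available 12-week data prior to dosing" and SAP 2.3 states it "for patients with available 12-week data prior to single dosing". The endpoint statements in Protocol 6.2.3 and SAP 3.2.3 do not repeat it.

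SAP 9.6 plans a summary table of patients with antibiotic-treated cholangitis episodes "in the 12 weeks prior to single dosing versus the 12-week treatment period will be presented for the Safety Analysis Set". It adds that the pre-dose information is recorded on the single-dose day as a look-back over 12 weeks, and that a listing for the same set will support the table. It names no subset and no denominator.

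Three other provisions decide what the table would show:

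- SAP 4.3.3: "The safety analysis set will include all patients who received at least 1 dose of A3907".
- SAP 3.3.1 (also Protocol 5.4 and 7.1.1): a patient whose single-dose exposure exceeds the highest seen in the first-in-human study is terminated before the 12-week period. SAP 3.1 allows such patients to be replaced.
- SAP Section 4: "The denominator for all percentages will be the number of patients in that treatment arm within the population of interest, unless otherwise specified". The same section allows a row for missing values where the shells call for one.

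**The concern.** The Safety Analysis Set can hold two kinds of patient who are not observed in both periods. Those stopped after the single dose have a pre-dose history but no 12-week treatment period. Any patient without a usable 12-week history has a treatment period but no comparator. The wording of the objective anticipates the second kind.

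If both columns are divided by the whole set, each kind pulls down the percentage in the period where it was not observed. The first makes an inactive drug look protective and the second makes it look harmful. The study has no control arm, so this before/after contrast is its planned evidence on the cholangitis objective. The difference between the columns would then partly reflect who was observed.

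**Working it through.** The documents give no event rate, effect size or power figure for this endpoint, so there is no planned figure to reproduce. The planned total is consistent: 4 arms × 6 = 24.

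**Inputs from the documents**

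- n = 6 patients per arm entering the 12-week period, 24 overall (Protocol 7.2.1, SAP 4.1).
- Denominator = all patients of the arm in the Safety Analysis Set (SAP Section 4 default; SAP 9.6 gives no other).

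**Inputs assumed**

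- p = true proportion with an episode, equal in both periods and in all patients (no drug effect).
- k = patients dosed once, stopped and replaced. They have full pre-dose data but no treatment period.
- m = treated patients without a usable 12-week history.
- All treated patients complete 12 weeks.

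**Patients stopped after the single dose (m = 0)**

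Pre-dose percentage: p(n + k)/(n + k) = p. Treatment-period percentage: p·n/(n + k). Apparent relative change: n/(n + k) − 1 = −k/(n + k).

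| | k | Relative change |
|---|---|---|
| Per arm, n = 6 | 1 | −1/7 = −14.3% |
| | 2 | −2/8 = −25.0% |
| | 3 | −3/9 = −33.3% |
| Overall, n = 24 | 2 | −2/26 = −7.7% |
| | 4 | −4/28 = −14.3% |
| | 6 | −6/30 = −20.0% |
| | 8 | −8/32 = −25.0% |

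The relative change does not depend on p. For example, with p = 25%, n = 6 and k = 2, the table would show 25.0% before and 0.25 × 6/8 = 18.8% during treatment.

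**Missing pre-dose history (k = 0)**

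Pre-dose percentage: p(n − m)/n. Treatment-period percentage: p. Apparent relative change: n/(n − m) − 1 = m/(n − m).

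| | m | Relative change |
|---|---|---|
| Per arm, n = 6 | 1 | 1/5 = +20.0% |
| | 2 | 2/4 = +50.0% |
| Overall, n = 24 | 2 | 2/22 = +9.1% |
| | 4 | 4/20 = +20.0% |
| | 6 | 6/18 = +33.3% |

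**After the fix**

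If both columns use only patients observed in both periods, each percentage equals p and the relative change is 0% for every k and m. It is also 0% without the fix when k = m = 0.

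**How other sections handle this**

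SAP 9.7, 9.9 and 9.10 limit their baseline 2 tables to patients who went on into the 12-week period, and SAP 7.3.1 does the same for 12-week exposure percentages. The baseline 1 tables in 9.7, 9.9 and 9.10 use the full Safety Analysis Set, as 9.6 does. SAP 9.3 calculates change in vital signs only where both the baseline and the later value exist. The SAP therefore already has the tools needed, but applies none of them in 9.6.

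**The case against.** Much of the case on the other side stands.

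- **The choice of set follows the protocol.** Protocol 10.2.3 assigns all exploratory endpoints other than PD to the safety analysis set, so SAP 9.6 is not an unexplained departure. That holds. But a subset of the Safety Analysis Set would satisfy both Protocol 10.2.3 and the restricted objective, whereas the present text satisfies only the former.
- **No rule classes unobserved patients as free of episodes.** A reader might infer one, but neither document states it. Protocol 10.2.2.2 says missing observations are in general not imputed, and the shells might add a row for missing values or set another denominator. What remains is arithmetic: under the default, the patient is in the denominator and cannot be in the numerator. A row for missing values would disclose this without changing the percentage.
- **SAP 9.6 is not out of line with all other 12-week summaries.** The limit to patients entering treatment applies to the baseline 2 tables and the 12-week exposure and compliance outputs. The cholangitis table is a baseline 1 comparison and matches its baseline 1 counterparts.
- **It cannot be said that the comparison is not within-patient.** SAP 9.6 does not fix the layout. The listing for the full set lets each patient's two periods be read side by side, and counts are unaffected by the denominator.
- **The inputs are assumed.** No rate of stopping for exposure is given. Missing histories are less certain than missing treatment periods, because the look-back is taken at a scheduled visit and screening already covers recent cholangitis.
- **Another asymmetry would remain.** Exclusion 15 bars bacterial cholangitis in the 60 days before Screening, so 60 of the 84 pre-dose days (71%) are largely closed to such events and about 24 are open. Pre-dose counts may be close to zero, and no choice of denominator cures that.

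**Conclusion.** The point holds as a minor one. The population of the objective and that of the table differ, and SAP 9.6 sets no denominator of its own. Followed literally, the plan lets patients unobserved in a period lower that period's percentage. The treatment-period gap is the firmer of the two, because the design itself provides for dosed patients who never enter that period.

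The figures of 14%, 25% and 33% apparent reduction, and 20% and 50% apparent increase, illustrate a no-effect scenario with six treated patients per arm. They are not forecasts. They rest on assumed numbers of unobserved patients and on the Section 4 default applying, which the shells could override. If every dosed patient is observed in both periods, nothing is distorted.

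The endpoint is exploratory and descriptive, with no test attached, so the consequence is confined to how the percentages are read. The primary safety analysis and the secondary endpoints are not affected.

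**What to change.** In SAP 9.6, define the comparison on those members of the Safety Analysis Set who have 12 weeks of pre-dose cholangitis data and who went on into the 12-week treatment period. Then:

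- use that one group as the denominator of both columns;
- report how many patients were left out, by reason (no pre-dose history; did not enter the treatment period);
- show the treatment-period follow-up actually observed, or flag patients who stopped before Week 12, so that an early stopper is not read as 12 weeks without an episode;
- keep the supporting listing on the full Safety Analysis Set.

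The cost is a revised sentence or two, a subset flag and a footnote. No new data are needed. The downside is a slightly smaller n in the table.
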